- 1. Freeze and transport samples to lab for temporary storage
- 2. Lyse, amplify, and sequence samples, then store sequences 5. Relevant chart review and record data for each participant
- 3. Analyze sequences with R statistical packages
- 4. Monitor for harms in clinic at visit and treat accordingly
- 6. Statistical analysis of sampled microbiomes by R packages

- Recruitment: During the spring of 2022, 80 patients of the UF Oaks Eye Clinic who meet inclusion criteria will be identified by study staff prior to their visit by chart review using the Epic electronic medical record and clinic scheduler on a secure encrypted UF computer. Up to 20 participants are expected to drop out over the course of this study. When patients have completed their clinical workup, [name] will approach patients without exclusion criteria to ascertain willingness/interest in the study, then recruit them. Study staff will give willing participants the appropriate informed consent form and counsel participants for consent to enroll in a private examination room. Completed consent forms will labelled with the participant's randomly selected numerical identifier as described below and stored securely in the UF Oaks Eye Clinic Office.
- Participant Criteria: This study includes adults above age 18 of either sex who can self-administer artificial tears and are scheduled to return for clinical follow-up in 1 week. This study excludes individuals with active eye infections, have prosthetic eyes, are immunocompromised, or are diagnosed with autoimmune diseases or malignant neoplasms about the eye. Individuals who take immunomodulatory therapy, steroids, antibiotics, medicated eyedrops, or are already using CMC artificial tears within 1 week of the study will also be excluded. These criteria maximize the number of self-consenting participants while minimizing participants whose compliance, conditions, or medications may change the eye microbiome.

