- Research Intervention: Participants will be given either artificial tears without CMC (control) or commercial artificial tears containing CMC (treatment) and told that they may have received either CMC or a placebo. Both are FDA-approved for over-the-counter use and for treatment of dry eye. Both interventions are standard therapies for dry eye disease. Prospective participants have the option to not enroll in the study, and the alternative is to complete a normal clinic visit. Individuals for whom artificial tears do not constitute standard therapy are excluded from this study.
- Assignment: This study design will include an experimental control, random assignment, and double blinding of staff and participants. The principal investigator will create a securely saved Excel spreadsheet with unique randomly generated numerical identifiers keyed to either the control group receiving artificial tears without CMC or the treatment group receiving CMC artificial tears. The principal investigator will then create plain cardboard boxes with the identifier on removable adhesive labels. Boxes will contain a copy of the informed consent form, participant instructions, and 21 plastic vials of either artificial tears without CMC or CMC artificial tears as assigned on the identifier spreadsheet. Patients will be blinded to their assigned intervention group. Study staff other than the principal investigator, who are blinded to box contents, will give participants a randomly selected box and an electronic survey (PDF) on an encrypted clinic computer in their private examination room. Labels will be placed on consent forms and identifiers will replace personal identifying information on electronic surveys.
- **Data Collection:** Electronic surveys will contain the Ocular Surface Disease Index and a box for entry of the patient's unique identifier. After completion of the survey, licensed physicians serving as study staff will swab the participant's right and left eye conjunctiva with a single cotton tip applicator, seal the applicator in a sample

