- tube, attach a label, and freeze it for storage in dry ice. The participant will complete a normal clinical schedule afterwards and will be scheduled to return in 1 week. Upon 1 week follow-up, participants will be swabbed again and complete a second survey. The second survey will be identical to the first survey but contain an additional question quantifying eye drop use to measure compliance. Patients will complete a normal clinical schedule afterwards. Study staff will correlate identifiers to patients using the informed consent forms and record ophthalmic history, ophthalmic medications, age, gender, tobacco usage, diabetes status, and race by chart review during this study.
- Sample Processing and Data Analysis: Samples will be frozen at -80 degrees Celsius and transported to a BSL-2 lab at UF for processing. During processing, samples will be lysed, amplified, and sequenced for bacterial 16S RNA using protocol supplied by Illumina MiSeq. Swabs and container tubes will be destroyed after sequencing. The sequenced bacterial microbiome of each sample will then be trimmed, error-corrected, and classified using the DADA2 R package as described in the article described above (Newsome 2021). After all samples are sequenced, microbiomes will be grouped by principal coordinate analysis using the phyloseq R package. Shannon's diversity indices will be calculated using the phyloseq R package. Differences in alpha diversity before and after treatment will be tested by PERMANOVA using the vegan R package, and differences in beta diversity will be tested by ANOVA using the nlme R package.
- Data Security: The original consent forms with unique identifier stickers will be kept securely in a folder and stored in a locked office within the UF Oaks Eye Clinic. Surveys will be accomplished on a pdf and do not contain any participant identification aside from the study-assigned numerical identifier. All other documents and data files will be deidentified and stored on an encrypted computer within the UF IT environment. Only medical students, resident physicians, and attending physicians serving as study staff will access participant medical records on the Epic EMR using a secure encrypted computer or smartphone. This study will not have a Data Safety Monitoring Board. [name] will serve as oversight for this research project and will meet weekly with study staff to monitor study conduct and patient safety.

7. Possible Discomforts and Risks:

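### The before/after PERMANOVA specifies no participant block although each completer gives two swabs; run as named, it is too conservative and loses power

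*Combined protocol and SAP*

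**What the plan says.** All references are to section 6 (Research Plan) of the combined protocol and SAP.

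- **Sampling (Data Collection).** At each visit staff "swab the participant's right and left eye conjunctiva with a single cotton tip applicator", so a visit yields one sample. Then: "Upon 1 week follow-up, participants will be swabbed again and complete a second survey". A completer therefore contributes two samples.
- **Analysis (Sample Processing and Data Analysis).** "Shannon's diversity indices will be calculated using the phyloseq R package". The tests follow in one sentence, which opens: "Differences in alpha diversity before and after treatment will be tested by PERMANOVA using the vegan R package". Its second half turns to the other measure: "differences in beta diversity will be tested by ANOVA using the nlme R package". No model formula, distance, participant term, permutation scheme or random effect is given, and there is no rule for people with only a first swab.
- **Numbers (Recruitment).** "80 patients of the UF Oaks Eye Clinic who meet inclusion criteria will be identified by study staff prior to their visit", and "Up to 20 participants are expected to drop out over the course of this study".
- **Arms (Assignment).** Identifiers are "keyed to either the control group receiving artificial tears without CMC or the treatment group receiving CMC artificial tears". The allocation ratio is not stated, and the analysis sentence does not mention the arms.

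**The concern.** Two swabs from the same eyes a week apart are likely to resemble each other more than swabs from different people. A before/after comparison should use that pairing. PERMANOVA in vegan shuffles all samples freely unless it is given a restriction, so an analyst who follows the sentence literally would treat the swabs as coming from different people. The reference distribution then contains between-person variation that the within-person contrast does not have, p-values come out too large, and a real change is more easily missed.

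Two related gaps add to this. First, a before/after test does not answer the randomised question, which is whether the change differs between CMC and control. The right permutation differs by contrast: visit varies within a person, while arm is constant within a person. Second, if people who leave after the first swab differ from those who stay, an unblocked comparison of all first swabs with the remaining second swabs can show a difference when nobody has changed.

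**Working it through.** The plan states no power, alpha or sample-size calculation, so there is no figure to reproduce.

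**Inputs from the documents:** 80 patients; up to 20 drop-outs, so 80 − 20 = 60 pairs; one sample per visit; two visits; two arms.

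**Assumptions (not in the documents):** 80 are enrolled and swabbed, and all 20 drop-outs leave after the first swab (an upper limit on unpartnered swabs); two-sided 5% test; unit SD; within-person correlation r of 0 to 0.7; a before/after shift of 0.4 SD; 1:1 allocation where arms are involved.

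**1. Unblocked before/after test, Shannon-type outcome (normal approximation).**

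- Variance the test assumes: 1/80 + 1/60 = 0.02917, SE 0.1708. The critical difference is 1.96 × 0.1708 = 0.3347 SD.
- True variance: 0.02917 − 2r × 60/(80 × 60) = 0.02917 − 0.025r.
- Paired test on 60 pairs: variance 2(1 − r)/60.

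Example at r = 0.5. The true variance is 0.01667, SE 0.1291. Size = 2P(Z > 0.3347/0.1291) = 2P(Z > 2.59) = 1.0%. Power at 0.4 SD = P(Z > (0.3347 − 0.4)/0.1291) = P(Z > −0.51) = 69%. The paired SE is also 0.1291, so paired power = P(Z > 1.96 − 0.4/0.1291) = P(Z > −1.14) = 87%.

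| r | Size, unblocked | Power, unblocked 80/60 | Power, 60 pairs |
|---|---|---|---|
| 0 | 5.0% | 65% | 59% |
| 0.3 | 2.3% | 67% | 75% |
| 0.5 | 1.0% | 69% | 87% |
| 0.7 | 0.2% | 73% | 98% |

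The loss is about 7, 18 and 25 points at r = 0.3, 0.5 and 0.7. At r = 0 there is none.

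**2. Permutation check.** This used Euclidean PERMANOVA on a Shannon-type outcome, with 1,500 trials and 399 permutations; Monte Carlo error is about 0.6 points at 5%. Sizes are across r = 0 to 0.7; powers are at r = 0.3 / 0.5 / 0.7.

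- Free permutation: size 2.5% / 1.5% / 0.3% at r = 0.3 / 0.5 / 0.7; power 63% / 68% / 72%.
- Visit permuted within participant, 60 pairs only: size 4.2% to 5.7%; power 71% / 85% / 99%.
- The same with the 20 unpartnered swabs kept: size 4.5% to 5.6%; power 74% / 86% / 97%.

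**3. Informative drop-out, unblocked test, no change in anyone.** If the 20 drop-outs differ from completers by an assumed 0.5 SD, the before mean moves by (20/80) × 0.5 = 0.125 SD. The rejection rate is P(Z > (0.3347 − 0.125)/SE) + P(Z < −(0.3347 + 0.125)/SE), with SE the true value from step 1.

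- At r = 0: P(Z > 1.23) + P(Z < −2.69) = 11.3%.
- At r = 0.3 / 0.5 / 0.7: 7.8% / 5.2% / 2.6%.
- With an assumed 1 SD difference (mean shift 0.25 SD): 31% / 28% / 26% / 22% at r = 0 / 0.3 / 0.5 / 0.7.

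**4. Arm-by-visit contrast, if freely permuted (30 pairs per arm).** The test assumes variance 4/30; the true variance is 4(1 − r)/30. Size = 2P(Z > 1.96/√(1 − r)) = 1.9% / 0.6% / 0.03% at r = 0.3 / 0.5 / 0.7. The plan does not name this contrast; the figures show only that the same omission would affect it.

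**The case against.** **The plan is silent; it does not decide against a block.** A reader might infer that an unblocked PERMANOVA was chosen. The documents do not support that. One summary sentence names a test and a package, frames the contrast as before against after, and names nlme, which can fit participant effects. This objection stands: the fault is that the pairing is unspecified. The gap still matters, because the literal reading gives the worse test.

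**The p-values are not shown to be wrong in both directions.** With uninformative drop-out the stated before/after test errs only towards conservatism. An excess of false positives would also arise if arm were tested as a main effect on pooled swabs, but the plan names no such test. For the stated test, the excess needs informative drop-out (step 3), and at 0.5 SD with r = 0.5 the rate is close to nominal.

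**Unpartnered first swabs need not be excluded.** Under within-participant permutation they do not move, and step 2 shows the size is held with them in. This stands. The figure of 20 is also an upper limit: the Recruitment paragraph speaks of 80 patients identified, not 80 enrolled.

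**Alpha and beta may have been swapped.** A distance-based test is assigned to scalar alpha diversity and ANOVA to beta diversity. If that is a swap, Shannon diversity would go to nlme, the Shannon figures above would no longer describe the PERMANOVA, and the blocking question would move to beta diversity. This is fair, but the pairing has to be respected either way. Simulations on invented genus abundances with Bray-Curtis distance point the same way for the before/after test; their sizes depend on made-up data and are not relied on here.

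**Conclusion.** The point holds as an unspecified pairing that should be settled before the data are analysed. If the named PERMANOVA is run with free permutation, it is conservative for any positive within-person correlation, and at a 0.4 SD shift it gives up roughly 7 to 25 points of power for correlations of 0.3 to 0.7. Power is reduced, not abolished, and at zero correlation nothing is lost from ignoring the pairing. If drop-outs differ by 0.5 SD, the error rate moves to about 11% / 8% / 5% / 3% at correlations of 0 / 0.3 / 0.5 / 0.7.

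The correlation, the shift, the drop-out difference and the enrolment of 80 are all assumptions, so these figures show a range and do not predict this trial's result. The absence of a block, and of any test tied to the CMC-versus-control contrast, is on the face of the text and needs no assumption.

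**What to change.** Add to Sample Processing and Data Analysis:

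1. Any visit term in PERMANOVA is tested by permuting visit within participant. State whether unpartnered baseline swabs stay in or are left out; either is valid under this restriction.
2. The arm-by-visit term, which answers the randomised question, is tested by permuting arm between whole participants, with both swabs moving together, in participants who have both swabs.
3. Models fitted in nlme carry a random participant intercept.
4. State which diversity measure each test is applied to, and correct the assignment if alpha and beta were exchanged.

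**Cost:** a few sentences and a few lines of R, with no effect on patients, samples or budget. The one downside is that participants with a single swab add nothing to the arm-by-visit PERMANOVA.

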Therefore, we hypothesize that the use of CMC in artificial tears may affect the eye microbiome and influence ocular diseases. Similar studies on microbiome composition used bacterial ribosomal RNA sequencing and statistical analysis with existing R packages such as phyloseg and DADA2. A UF investigator, [name], recently conducted a microbiome study entitled "The gut microbiome of COVID-19 recovered patients returns to uninfected status in a minority dominated United States cohort" at the University of Florida in 2021. For these reasons, we are conducting a similar study on the use of artificial tears containing CMC compared to control artificial tears without CMC. Results of this study will lead to a better understanding of the risks and benefits associated with CMC artificial tears for eye lubrication and dry eye disease.

5. Specific Aims:

We aim to examine whether carboxymethylcellulose in artificial tears changes the eye microbiome and identify which bacterial genera are enriched.

6. Research Plan:

Before Study Enrollment

- 1. Staff creates Excel key and labels with identifiers
- 2. Screen clinic schedule for inclusion and exclusion criteria
- 3. Study staff assigns and labels cardboard boxes with numerical identifiers, then attaches spare labels
- 4. Principal investigator fills boxes with control or CMC artificial tears, consent copies, and patient instructions, then seals the boxes with tape
- 5. Store boxes on-site for staff

Initial Study Schedule

- 1. Participant checks into clinic and receives clinical workup
- 2. [name] approaches, recruits, and enrolls patient.
- 3. Staff ensures patient meets criteria at time of visit
- 4. Participant signs consent form
- 5. Staff gives a random box to the participant and attaches box label to informed consent form
- 6. Participant completes survey 1
- 7. Licensed staff collect 1st swab
- 8. Participant has a normal clinic visit and is scheduled to return

Second Study Schedule

- 1. Participant checks into clinic and receives clinic workup 1 week after initial visit
- 2. If participant does not have box labels, the informed consent form label is consulted to associate surveys and data
- 3. Participant completes survey 2
- 4. Staff ensures that both surveys are completed and recorded
- 5. Licensed staff collects 2nd swab
- 6. Participant completes a normal clinic visit and has thereafter completed the study

Tasks Throughout Study Duration

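### No between-arm model adjusts week-1 Shannon diversity for its swab-1 value; if the arms are compared on change scores, the effective sample lost is (1−r)/2

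*Combined protocol and SAP*

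**What the plan says.** The whole analysis plan is the paragraph on sample processing and data analysis in section 6 (Research Plan). On alpha diversity it states that "Shannon's diversity indices will be calculated using the phyloseq R package" and that "Differences in alpha diversity before and after treatment will be tested by PERMANOVA", with the vegan package. Beta diversity is assigned to ANOVA in the nlme package. For neither outcome is there a model formula, arm contrast, pairing, random effect or covariate.

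The data needed for adjustment are already planned. Step 7 of the initial study schedule reads "Licensed staff collect 1st swab", and the data collection paragraph adds: "Upon 1 week follow-up, participants will be swabbed again and complete a second survey". Each completer therefore has one value at each visit. The box is handed over two steps before the first swab, but the schedule lists no drop use in between, and the analysis treats that swab as the before-treatment sample.

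On design, identifiers are "keyed to either the control group receiving artificial tears without CMC or the treatment group receiving CMC artificial tears"; no allocation ratio is given. On size, "80 patients of the UF Oaks Eye Clinic who meet inclusion criteria will be identified by study staff" and "Up to 20 participants are expected to drop out over the course of this study". No correlation, SD, effect size, significance level or power is stated.

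**The concern.** The trial is randomised and controlled, so its main result on Shannon diversity should be a difference between arms. The only use the plan states for swab 1 is as the earlier half of a before-after difference. The obvious way to turn that into an arm comparison is to compare mean change between arms. Doing so fixes the baseline coefficient at 1, whereas a baseline-adjusted model estimates it. Apart from the degree of freedom spent on the slope, the adjusted estimate is never less precise.

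Three things are at stake:

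- **Precision.** The plan expects about 60 completers and gives no sample-size justification, so there is little to spare. With equal SDs, a change score is worse than ignoring swab 1 altogether when r is below 0.5.
- **Chance imbalance.** In small arms, a chance difference in baseline Shannon carries into the change-score result through regression to the mean.
- **Prespecification.** With no model written down, the analyst can choose among post-only, change and adjusted results after seeing the data.

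**Working it through.** **Inputs from the documents.** 80 patients, up to 20 dropouts, hence 80 − 20 = 60 completers; two arms; one swab before and one at 1 week. There is no power calculation to reproduce.

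**Inputs assumed.** 1:1 allocation, so n = 30 completers per arm; two-sided 5% level; 80% power; SD of Shannon equal at both visits and set to 1; r from 0.3 to 0.7.

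**Variance of the arm effect**, in units of 2·SD²/n:
- change score: 2(1−r)
- baseline-adjusted: 1−r²
- week-1 value alone: 1

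The ratio of change to adjusted is 2(1−r)/(1−r²) = 2/(1+r). The share of effective sample lost is 1 − (1+r)/2 = (1−r)/2.

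| r | Change | Adjusted | Ratio | Lost | 60 completers worth |
|---|---|---|---|---|---|
| 0.3 | 1.40 | 0.91 | 1.54 | 35% | 39 |
| 0.5 | 1.00 | 0.75 | 1.33 | 25% | 45 |
| 0.7 | 0.60 | 0.51 | 1.18 | 15% | 51 |

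The cost of estimating the slope trims the loss slightly. A simulation with 30 per arm and 20,000 runs gave 33%, 24% and 14%.

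**Detectable difference at 80% power**, from the noncentral t with 58 df (change, week-1 alone) or 57 df (adjusted), in SD units:

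| r | Change | Adjusted | Week-1 alone |
|---|---|---|---|
| 0.3 | 0.87 | 0.70 | 0.74 |
| 0.5 | 0.74 | 0.64 | 0.74 |
| 0.7 | 0.57 | 0.53 | 0.74 |

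For a true difference of 0.7 SD at r = 0.3, power is about 62% on change and 80% adjusted.

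**Sensitivity to r.** Under equal SDs the loss is 50% at r = 0, 40% at 0.2, 10% at 0.8 and 5% at 0.9.

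**Sensitivity to the SDs.** Let k be the post/pre SD ratio. The loss is 1 − k²(1−r²)/(1 + k² − 2rk).

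| k | r = 0.3 | r = 0.5 | r = 0.7 |
|---|---|---|---|
| 0.8 | 50% | 43% | 37% |
| 1 | 35% | 25% | 15% |
| 1.25 | 22% | 11% | 2% |

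The change score is worse than week-1 alone when 1 + k² − 2rk exceeds k², that is when r < 1/(2k): below 0.625, 0.5 and 0.4 for the three rows.

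**Scope of the formula.** It applies to an arm comparison of change, and to its equivalent, an arm-by-time model with unconstrained baseline means fitted to complete pairs. A model that constrains both arms to one baseline mean recovers about the efficiency of adjustment.

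**The case against.** The strongest reply is that the plan never says the arms will be compared on change. Its sentence could equally describe a pooled before-after test, tests within each arm, or a model with arm and time. Under a pooled or within-arm reading there is no arm estimate, and the efficiency ratio has nothing to apply to. The larger gap is then the missing randomised contrast. This stands, and it is why the loss must be stated conditionally. It does not remove the point: adding an arm term to a before-after difference would supply the contrast and leave the inefficiency in place.

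A second reply is that nlme fits mixed models and could handle the baseline efficiently. The plan pairs PERMANOVA with alpha diversity and ANOVA in nlme with beta diversity, which looks transposed, so Shannon may have been meant for nlme. That is possible and should be clarified first. As written, nlme is assigned to beta diversity with no terms, and naming a package does not fix how the baseline enters.

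A reader might also infer that this trial wastes 15 to 35% of its sample. The documents do not support that: the range merely restates an assumed r of 0.7 down to 0.3 with equal SDs. Nor do they support the claim that no analysis will adjust, only that none is specified. A change-score comparison would not be invalid either, since under randomisation it remains unbiased. Finally, nothing here rules out reporting before-after change. The stated aim is whether CMC changes the eye microbiome, and describing change within each arm is legitimate.

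**Conclusion.** The point holds in conditional form. The plan specifies no between-arm model that adjusts week-1 Shannon for swab 1, and its only stated use of swab 1 for Shannon is as the before value. If the arms are compared on change, or by the equivalent unconstrained model, the loss is (1−r)/2 under equal SDs. The practical gain from adjustment is sizeable at r = 0.3 and small at r = 0.7, where the detectable difference moves only from 0.57 to 0.53 SD. The direction does not depend on r or the SDs, apart from one degree of freedom; the size depends on both, and on the assumed 30 per arm. This is a matter of efficiency and prespecification for Shannon diversity. It does not extend to distance-based beta diversity.

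**What to change.** First clarify which test belongs to which outcome. Then add one sentence to the analysis paragraph: the arm comparison for Shannon diversity is a linear model of the week-1 index on randomised arm with the swab-1 index as covariate, reported as the adjusted arm difference with its 95% confidence interval. An acceptable alternative is an nlme model of both visits with a common baseline mean for the two arms (visit and arm-by-visit terms, no arm difference at swab 1).

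Change within each arm may be reported descriptively but should not serve as the arm contrast.

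The cost is one degree of freedom (57 in place of 58 with 60 completers) and a sentence of text. It needs no extra swab, visit or participant.
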